7.2 Demographic and Other Baseline Characteristics

7.2.1 Demographics

At Screening, the following demographic data will be collected: date of birth, sex (gender), weight, height, race, and ethnicity.

Demographic data collected at Screening will be recorded in the eCRF.

7.2.2 Medical History

A complete review of the subject's medical history (including the hepatic insufficiency) should be performed at Screening to determine the subject's eligibility. An update of medical history will be performed at admission to the study center on Day -1. At Screening, subjects with hepatic impairment will be allocated to the mild (Child-Pugh class A) and moderate (Child-Pugh class B) hepatic impairment group according to the Child-Pugh classification as specified in Table 2 and Table 3.

7.2.3 Medication History

The medication history of subjects must be collected at Screening and updated at admission to the study center. See Section 6.5 for details regarding permitted and prohibited medications.

7.2.4 Other Baseline Assessments

All other baseline measurements, such as vital signs, height and weight, a complete physical examination, clinical laboratory parameters, alcohol breathalyzer test, cotinine test, drugs of abuse screen, pregnancy test in women, FSH levels in postmenopausal women, and 12-lead ECGs will

be assessed at timepoints as specified in the Schedule of Assessments for Part 1 and Part 2 (Table 1).

7.3 Efficacy Assessments

Not applicable

7.4 Assessment of Safety

Subjects will be admitted to the study center on Day -1 and closely monitored for AEs after administration of the IMP. The safety profile of tepotinib will be assessed through the recording, reporting and analysis of baseline medical conditions, AEs, physical examination findings including vital signs, 12-lead ECG recordings, and laboratory tests. Pre-existing conditions that are present before the IMP administration will be recorded as baseline conditions.

Comprehensive assessment of any apparent toxicity experienced by each subject will be performed from the time of giving informed consent and throughout the study. The Investigator will report any AEs, whether observed by the Investigator or reported by the subject (see Section 7.4.1.2). The reporting period for AEs is described in Section 7.4.1.3.

7.4.1 Adverse Events

7.4.1.1 Adverse Event Definitions

Adverse Event

An AE is any untoward medical occurrence in a subject or clinical investigation subject administered a pharmaceutical product, regardless of causal relationship with this treatment. An AE can therefore be any unfavorable and unintended sign (including an abnormal laboratory finding), symptom, or disease temporally associated with the use of a medicinal product, whether or not considered related to the medicinal product.

For surgical or diagnostic procedures, the condition/illness leading to such a procedure is considered as the AE rather than the procedure itself.

The Investigators are required to grade the severity or toxicity of each AE.

Investigators will reference the most recent version of the National Cancer Institute (NCI) - Common Terminology Criteria for Adverse Events (CTCAE), a descriptive terminology that can be used for AE reporting when describing AEs.

A general grading (severity/intensity; hereafter referred to as severity) scale is provided at the beginning of the above referenced document, and specific event grades are also provided.

If a particular AE's severity is not specifically graded by the guidance document, the Investigator is to use the general NCI-CTCAE definitions of Grade 1 through Grade 5 following his or her best medical judgment.

MS200095-0028

The 5 general grades are:

- Grade 1 or Mild
- Grade 2 or Moderate
- Grade 3 or Severe
- Grade 4 or Life-threatening
- Grade 5 or Death

According to Sponsor convention, any clinical AE with severity of Grade 4 or 5 must also be reported as an SAE. However, a laboratory abnormality of Grade 4, such as anemia or neutropenia, is considered serious only if the condition meets one of the serious criteria described below.

If death occurs, the primary cause of death or event leading to death should be recorded and reported as an SAE. "Fatal" will be recorded as the outcome of this specific event and death will not be recorded as separate event. Only, if no cause of death can be reported (for example, sudden death, unexplained death), the death per se might then be reported as an SAE.

Investigators must also systematically assess the causal relationship of AEs to the IMP using the following definitions. Decisive factors for the assessment of causal relationship of an AE to the IMP include, but may not be limited to, temporal relationship between the AE and the IMP, known side effects of the IMP, medical history, concomitant medication, course of the underlying disease, study procedures.

Unrelated: Not reasonably related to the IMP. The AE could not medically (pharmacologically/clinically) be attributed to the IMP under study in this clinical study protocol. A reasonable alternative explanation must be available.

Related: Reasonably the IMP The AE could medically related to (pharmacologically/clinically) be attributed to the IMP under study in this clinical study protocol.

Abnormal Laboratory Findings and Other Abnormal Investigational Findings

Abnormal laboratory findings and other abnormal investigational findings (for example, on an ECG trace) should not be reported as AEs unless they are associated with clinical signs and symptoms, lead to treatment discontinuation or are considered otherwise medically important by the Investigators. If a laboratory abnormality fulfills these criteria, the identified medical condition (for example, anemia, or increased alanine aminotransferase) must be reported as the AE rather than the abnormal value itself.

Serious Adverse Events

An SAE is any untoward medical occurrence that at any dose:

• Results in death

- Is life-threatening (Note: The term "life-threatening" refers to an event in which the subject is at risk of death at the time of the event, not an event that hypothetically might have caused death if it was more severe.)
- Requires inpatient hospitalization or prolongs an existing hospitalization
- Results in persistent or significant disability or incapacity
- Is a congenital anomaly or birth defect
- Is otherwise considered to be medically important. (Note: Important medical events that may not result in death, be life-threatening, or require hospitalization may be considered as SAEs when, based upon appropriate medical judgment, they may jeopardize the subject or may require medical or surgical intervention to prevent one of the outcomes listed above. Examples of such events include allergic bronchospasm requiring intensive treatment in an emergency room or at home, blood dyscrasias or convulsions that do not result in inpatient hospitalization, or the development of drug dependency or drug abuse.)

For the purposes of reporting, any suspected transmission of an infectious agent via an IMP is also considered an SAE, as described in Section 7.4.1.4.

Events that Do Not Meet the Definition of an SAE

Elective hospitalizations to administer, or to simplify study treatment or study procedures (for example, an overnight stay to facilitate chemotherapy and related hydration therapy application) are not considered SAEs. However, all events leading to unplanned hospitalizations or unplanned prolongation of an elective hospitalization (for example, undesirable effects of any administered treatment) must be documented and reported as SAEs.

Events Not to Be Considered as AEs/SAEs

Medical conditions present at the Screening visit that do not worsen in severity or frequency during the study are defined as Baseline Medical Conditions, and are not to be considered AEs.

Adverse Events of Special Interest

No AEs of special interest have been defined.

7.4.1.2 Methods of Recording and Assessing Adverse Events

At each study visit, the subject will be queried on changes in his or her condition. During the reporting period, any unfavorable changes in the subject's condition will be recorded as AEs, whether reported by the subject or observed by the Investigator.

Subjects will be educated to inform the study staff of any AE they may be experiencing, as they occur. While the subjects are confined to the study center, study staff will solicit responses from subjects daily for any AEs or any changes to their health in general. Furthermore, any changes in safety monitoring (eg, vital signs, laboratory results, etc), notable as AEs through review by the Investigator/designee, will be recorded accordingly.

Complete, accurate and consistent data on all AEs experienced for the duration of the reporting period (defined below) will be reported on an ongoing basis in the appropriate section of the eCRF. All SAEs must be additionally documented and reported using the appropriate Report Form as described in Section 7.4.1.4.

It is important that each AE report include a description of the event, its duration (onset and resolution dates (and times when it is important to assess the time of AE onset relative to the recorded treatment administration time), its severity, its causal relationship with the IMP, any other potential causal factors, any treatment given or other action taken, including discontinuation of the IMP, and its outcome. In addition, serious cases should be identified and the appropriate seriousness criteria documented.

Specific guidance can be found in the eCRF Completion Guidelines provided by the CRO.

7.4.1.3 Definition of the Adverse Event Reporting Period

The AE reporting period for safety surveillance begins when the subject is initially included in the study (date of first signature of informed consent/) and continues until the End of Study visit.

Any SAE assessed as related to the IMP must be reported whenever it occurs, irrespective of the time elapsed since the last administration of the IMP.

7.4.1.4 Procedure for Reporting Serious Adverse Events

Serious Adverse Events

In the event of any new SAE occurring during the reporting period, the Investigator must immediately (within a maximum of 24 HOURS after becoming aware of the event) inform the Sponsor or its designee using the SAE Report Form following specific completion instructions.

In exceptional circumstances, an SAE (or follow-up information) may be reported by telephone; in these cases, an SAE Report Form must be provided immediately thereafter.

Relevant pages from the eCRF may be provided in parallel (for example, medical history, concomitant drugs). Additional documents may be provided by the Investigator, if available (for example, laboratory results, hospital report, autopsy report). In all cases, the information provided on the SAE Report Form must be consistent with the data about the event recorded in the eCRF.

The Investigator must respond to any request for follow-up information (for example, additional information, outcome, final evaluation, other records where needed) or to any question the Sponsor/designee may have on the AE within the same timelines as those noted above for initial reports. This is necessary to ensure prompt assessment of the event by the Sponsor or designee and (as applicable) to allow the Sponsor to meet strict regulatory timelines associated with expedited safety reporting obligations.

Requests for follow-up will usually be made via the responsible Monitor, although in exceptional circumstances the Global Drug Safety department may contact the Investigator directly to obtain further information or to discuss the event.

7.4.1.5 Safety Reporting to Health Authorities, Institutional Review Boards and Investigators

The Sponsor will send appropriate safety notifications to Health Authorities in accordance with applicable laws and regulations.

The Investigators must comply with any applicable study center-specific requirements related to the reporting of SAEs (particularly deaths) involving study subjects to the IRB that approved the study.

In accordance with ICH GCP, the Sponsor/designee will inform the Investigator of "findings that could adversely affect the safety of subjects, impact the conduct of the study or alter the IRB's approval/favorable opinion to continue the study." In particular and in line with respective regulations, the Sponsor/designee will inform the Investigator of AEs that are both serious and unexpected and are considered to be related to the administered product ("suspected unexpected serious adverse reactions"). The Investigators should place copies of Safety Reports in the Investigator Site File. National regulations with regard to Safety Report notifications to Investigators will be taken into account.

When specifically required by regulations and guidelines, the Sponsor/designee will provide the appropriate Safety Reports directly to the concerned lead IRB and will maintain records of these notifications. When direct reporting is not clearly defined by national or study center-specific regulations, the Investigator will be responsible for promptly notifying the concerned IRB of any Safety Reports provided by the Sponsor/designee and of filing copies of all related correspondence in the Investigator Site File.

For studies covered by the European Directive 2001/20/EC, the Sponsor's responsibilities regarding the reporting of SAEs/suspected unexpected serious adverse reactions/Safety Issues will be carried out in accordance with that Directive and with the related Detailed Guidance documents.

7.4.1.6 Monitoring of Subjects with Adverse Events

AEs are recorded and assessed continuously throughout the study (see Section 7.4.1.3) and are assessed for final outcome at the End of Study visit. All SAEs ongoing at the End of Study visit must be monitored and followed up by the Investigators until stabilization or until the outcome is known, unless the subject is documented as "lost to follow-up". Reasonable attempts to obtain this information must be made and documented. It is also the responsibility of the Investigator to ensure that any necessary additional therapeutic measures and follow-up procedures are performed.

7.4.2 Pregnancy and In Utero Drug Exposure

Only pregnancies considered by the Investigator to be related to the IMP (for example, resulting from a drug interaction with a contraceptive medication) are considered to be AEs. However, all

pregnancies with an estimated conception date during the period defined in Section 7.4.1.3 must be recorded by convention in the AE page/section of the eCRF. The Investigator must notify the Sponsor/designee in an expedited manner of any pregnancy using the Pregnancy Report Form, which must be transmitted according to the same process as described for SAE reporting in Section 7.4.1.4.

Investigators must actively follow up, document and report on the outcome of all these pregnancies, even if the subjects are withdrawn from the study.

The Investigator must notify the Sponsor/designee of these outcomes using the Pregnancy Report Form. If an abnormal outcome occurs, the SAE Report Form will be used if the subject sustains an event and the Parent-Child/Fetus Adverse Event Report Form if the child/fetus sustains an event.

Any abnormal outcome must be reported in an expedited manner as described in Section 7.4.1.4, while normal outcomes must be reported within 45 days after delivery.

In the event of a pregnancy in a female subject occurring during the course of the study, the subject must be discontinued from study medication immediately.

In the unlikely event of a pregnancy in a female partner of a male subject occurring during the course of the study, The Sponsor/designee must be notified without delay. The Investigator will attempt to collect pregnancy information on any female partner who becomes pregnant while her male partner is participating in the study. The Investigator will request the necessary signed informed consent from the female partner and if the consent is provided, the Investigator will record pregnancy information on the appropriate form for submission to the Sponsor. If consent is provided, follow up on the pregnancy will continue through the delivery date or termination of the pregnancy, and information regarding the pregnancy outcome and fetal/infant status at outcome (presence or absence of anomalies) will be documented.

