5.1 Overall Study Design and Plan

This is a Phase 1, two-staged, open-label study to investigate the effect of various degrees of hepatic impairment on the PK, safety and tolerability of the c-Met kinase inhibitor, tepotinib.

Part 1 will include subjects with hepatic impairment (Child-Pugh class A [6 subjects] and Child-Pugh class B [6 subjects]) and a control group (6 healthy subjects matched 1:1 to 6 subjects with Child-Pugh class B with regard to age \pm 10 years, weight \pm 10 kg, and same gender). All subjects will receive a single dose of 500 mg tepotinib.

Part 2 of the study is optional and, if conducted, will evaluate doses above 500 mg up to 1000 mg in 6 subjects with hepatic impairment of either Child-Pugh class A or B.

An SMC may be established to evaluate the safety- and PK results of Part 1 if the overall development program of tepotinib decides to use higher doses than 500 mg (up to 1000 mg) in the Phase 2 or Phase 3 studies. The SMC will then make a recommendation on the tepotinib dose and which population (Child-Pugh class A or B) to be enrolled in Part 2 based on the safety- and PK results of Part 1. See Figure 1 for a diagram of the study design.

Subjects will be screened from Day -28 to Day -2. Subjects will be admitted to the study center on Day -1 and will remain inpatient at the study center under medical supervision until discharge on the morning of Day 4.

[figure not shown]
The treatment consists of a single-dose administration of 500 mg tepotinib on Day 1 in Part 1. The dose to be investigated in Part 2 will be determined by the SMC after evaluation of the safety- and PK results of Part 1.

Serial blood samples (PK and clinical laboratory assessments) and urine samples (clinical laboratory assessments) will be collected at the timepoints provided in Table 1. There is a PK sampling period of 2 weeks for healthy subjects and 3 weeks for hepatic impaired subjects.

The End of Study visit is planned on Day 15 for healthy subjects and on Day 22 for hepatic impaired subjects. An Early Termination visit will be conducted for subjects who withdraw

prematurely. The same assessments as for the End of Study visit will be conducted at the Early Termination visit.

Figure 1 Design Diagram

Part 2 of the study is optional.

CSR = Clinical study report; HCC = Hepatocellular carcinoma; PK = Pharmacokinetic, SMC = Safety Monitoring Committee.

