5.3.1 Inclusion Criteria

All subjects:

- 1. Men and women (of nonchildbearing potential), 18 to 75 years (inclusive) of age at Screening
- 2. Body mass index of 18 to 36 kg/m² (inclusive) with a body weight \geq 50 kg at Screening
- 3. Women must be postmenopausal for at least 1 year, as confirmed by follicle stimulating hormone (FSH) assessments performed at Screening, or surgically sterile (ie, documented hysterectomy, documented bilateral salpingectomy, or documented bilateral oophorectomy). Pregnancy assessments will also be performed on female subjects at Screening and at admission to the study center
- 4. A male participant must agree to use a barrier method, and to have their female partners use highly effective, medically acceptable methods of contraception (ie, methods with a failure rate of less than 1 % per year) as detailed in Appendix I of this protocol during participation in

the study and for at least 90 days after the last dose of IMP. Men must refrain from donating sperm during the same period

- 5. Heart rate in the range of 50 to 99 beats per minute after 10 minutes rest in the semi-supine position at Screening
- 6. Negative drug-screening results and a negative alcohol breathalyzer test at Screening and Day -1. For all subjects, a negative cannabinoid (THC) result on drugs of abuse screening is required to participate in the study. If the result is positive, the Principal Investigator may request to repeat the test. For subjects with hepatic impairment, a positive cannabinoid (THC) result on drugs of abuse screening will not be exclusionary (at Screening or Day -1) if the subject uses cannabinoids on medical recommendation. In subjects with hepatic impairment, positive test for drugs used on medical recommendation will be not exclusionary.
- 7. Negative human immunodeficiency virus 1 and 2 antibodies at Screening
- 8. Subject must have given written informed consent before any study-related activities are carried out and must be able to understand the full nature and purpose of the study, including possible risks and adverse effects
- 9. Absence of acute hepatitis.

Subjects with normal hepatic function:

- 10. Healthy volunteers, as judged by the Investigator
- 11. Medical history without any ongoing clinically relevant findings as judged by the Investigator
- 12. Physical examinations without any clinically relevant findings as judged by the Investigator.

Subjects with impaired hepatic function:

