6.2 Dosage and Administration

All subjects will receive the IMP once only in the course of the study. A single oral dose of 500 mg in Part 1 and up to 1000 mg in Part 2 tepotinib tablets will be administered to subjects after they have completed a standard breakfast. The IMP administration will occur 30 minutes after the start of the intake of a standard meal. Subjects should eat this meal within 25 minutes or less. The IMP will be administered with 240 mL of water. The subject will remain fasting for 4 hours after the breakfast, after which a standardized lunch will be served. Further details on the standard breakfast are provided in Section 6.5.3.

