(Sexual abstinence is considered a highly effective method only if defined as refraining from heterosexual intercourse during the entire period of risk associated with the study drug. The reliability of sexual abstinence needs to be evaluated in relation to the duration of the study and the preferred and usual lifestyle of the participant.)

NOTES:

- a) Typical use failure rates may differ from those when used consistently and correctly. Use should be consistent with local regulations regarding the use of contraceptive methods for participants participating in clinical studies.
- b) Hormonal contraception may be susceptible to interaction with the study drug, which may reduce the efficacy of the contraceptive method. In this case two highly effective methods of contraception should be utilized during the treatment period and for at least 90 days after the last dose of study treatment

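### The required recording of pregnancies stops at the End of Study visit (14 or 21 days after the dose), although the protocol asks male subjects for contraception for at least 90 days after it

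*Protocol*

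**What the plan says.** Four places in the protocol bear on this.

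- **Recording rule, Section 7.4.2.** All "pregnancies with an estimated conception date during the period defined in Section 7.4.1.3 must be recorded by convention", on the AE pages of the eCRF. The Investigator must follow the pregnancies so covered to outcome and report the result.
- **Length of the period, Section 7.4.1.3.** It starts at informed consent and "continues until the End of Study visit". Section 5.1 gives the date: "The End of Study visit is planned on Day 15 for healthy subjects and on Day 22 for hepatic impaired subjects".
- **Partner paragraph, Section 7.4.2.** It speaks of a partner pregnancy that occurs during the course of the study. It asks the Investigator to try to collect information on a partner who becomes pregnant "while her male partner is participating in the study".
- **Contraception period, Section 5.3.1, inclusion criterion 4.** Male subjects use a barrier method, and their partners highly effective contraception, during "the study and for at least 90 days after the last dose of IMP. Men must refrain from donating sperm during the same period". A note to Appendix I on hormonal contraception gives the same length, "for at least 90 days after the last dose of study treatment".

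Section 6.2 fixes the last dose as the first: "All subjects will receive the IMP once only in the course of the study". Section 5.1 places it on Day 1.

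**The concern.** The protocol asks couples to avoid conception for about three months after dosing, but ties pregnancy recording to a period that ends two or three weeks after dosing. If contraception failed on Day 40, say, the conception would fall inside the contraception period. It would fall outside both the eCRF recording rule and the partner paragraph.

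At stake is the information that Section 7.4.2 exists to collect: that a pregnancy occurred after exposure of the male subject, and how it ended. Section 3.1 shows why the sponsor cares about the subject at all. It cites teratogenic effects of c-Met inhibition in knockout mice, and uses them there to justify excluding women of childbearing potential. The point concerns safety reporting only.

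**Working it through.** The protocol gives no figure of its own on this mismatch, so there is none to reproduce. The check is date arithmetic.

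**Inputs**
- Dose: once, on Day 1 (Sections 5.1 and 6.2).
- End of the recording period: Day 15 (healthy) or Day 22 (hepatic impaired), from Sections 7.4.1.3 and 5.1.
- Contraception period: at least 90 days after the last dose, so to Day 91 or later (Section 5.3.1, criterion 4).

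**Formula**
Post-dose days covered = End of Study day − 1. Days not covered = 90 − days covered. Share = days not covered / 90.

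| Group | Covered | Not covered | Share of 90 days |
|---|---|---|---|
| Healthy | 15 − 1 = 14 | 90 − 14 = 76 | 76/90 = 84.4% |
| Hepatic impaired | 22 − 1 = 21 | 90 − 21 = 69 | 69/90 = 76.7% |

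Criterion 4 sets at least 90 days, so these are minimum shares.

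**Sensitivity to the denominator.** The AE period also covers screening. If a full 28 days of screening is added as covered time, the shares become 76/(90 + 28) = 64.4% and 69/(90 + 28) = 58.5%. Conceptions before dosing are not the issue, so the 90-day shares are the relevant ones. More than half of the window is uncovered either way.

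**How many pregnancies this could involve.** Assume that every subject is a man with a fertile partner. Assume also a failure rate of 1% per year, the ceiling that criterion 4 gives for highly effective methods, and no extra benefit from the barrier method.
- Part 1 (6 healthy, 12 impaired): 6 × 76 + 12 × 69 = 1,284 uncovered days; 1,284/365 = 3.52 person-years; × 0.01 = 0.035 pregnancies.
- Parts 1 and 2 (6 healthy, 18 impaired): 6 × 76 + 18 × 69 = 1,698 days; 1,698/365 = 4.65 person-years; × 0.01 = 0.047 pregnancies.

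Appendix I notes that typical-use failure rates may differ. The result scales in proportion: an assumed rate of 10% per year would give 0.35 and 0.47, still below one.

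**Does participation include the 90 days?** Criterion 4 names participation and the 90 days after dosing as two separate things, so the partner paragraph's limit to participation does not take in the 90 days. The words on the course of the study might be stretched to the end of the whole study, which Section 5.7 defines as the last subject's last visit. The window would then depend on enrolment order, and the last subject would gain nothing.

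**The case against.** The strongest objections come from other text in the same sections.

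- **An untimed duty to notify.** The sentence after the recording rule obliges the Investigator to tell the sponsor promptly about a pregnancy on the Pregnancy Report Form, and sets no period. The recording rule itself concerns entry on the AE pages. This stands in part. A reader might infer that late pregnancies would go unreported and the information be lost, and the text does not support that. But the partner paragraph, which covers the group that matters here, restates the time limit. Follow-up is required for the pregnancies just described, which leaves open whether late ones are among them.
- **Related SAEs.** Section 7.4.1.3 requires SAEs judged related to the IMP to be reported whenever they occur, and Section 7.4.1.1 counts congenital anomaly or birth defect as a seriousness criterion. A birth defect judged related would remain reportable. The rule does not require a late-conceived pregnancy to be recorded, or followed to an outcome that might then be judged.
- **No contradiction.** Contraception is a duty of the subject, and recording is a duty of the site. Both can be met in full, and no sentence promises 90 days of recording. This stands: the windows are mismatched, not contradictory.
- **Not a stated risk period.** The protocol sets the 90 days for contraception and sperm donation and does not call them a period of risk. Its teratogenicity statement makes no claim about exposure through male subjects. Sections 5.2 and 7.5.1 say that most healthy subjects are not expected to have measurable concentrations after Day 15. This also stands, but the mismatch does not depend on the label.
- **Few events, few people.** Women enrolled must be of nonchildbearing potential, so in practice only partners of male subjects are concerned, and the expected count is small. This limits the weight of the point.
- **Subject information.** The information sheet is not among the documents and may already ask men to report later pregnancies. Even so, the protocol text would still need to say what the site does with such a report.

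**Conclusion.** The point holds as a mismatch between two windows that the protocol sets for itself. For partners of male subjects, at least 84% (healthy) or 77% (impaired) of the 90 post-dose days lie outside the stated recording and follow-up window. This rests on the planned visit days and on reading participation as ending at the subject's End of Study visit.

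A reader might infer that most partner pregnancies at risk would be missed. The percentages do not show that. They measure calendar days, and reading them as a share of pregnancies would need conceptions spread evenly over the period. Under the assumptions above, the expected number in the uncovered time is about 0.035 to 0.047.

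What remains is an ambiguity. It is unclear whether a pregnancy conceived after the last visit but within the contraception period must be recorded, and no text clearly requires it to be followed to outcome. This is a low-cost improvement to safety reporting. It does not affect the PK endpoints, the analysis or the sample size.

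**What to change.** Reconcile Section 7.4.2, including the partner paragraph and the reference to Section 7.4.1.3, with inclusion criterion 4. Pregnancy notification and outcome follow-up would then cover conceptions during the contraception period that the protocol already sets. The AE reporting period can stay as it is if Section 7.4.2 states its own conception window. I take no view on how long the contraception period should be.

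Male subjects would be told at the End of Study visit, and in the subject information, to report a partner pregnancy conceived within that period. The existing partner-consent step and report forms can be used.

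The cost is wording in the protocol and, if it is not already there, in the subject information. No visit, sample or procedure is added. The downside is that the site must keep a reporting channel open after the last visit, for at least 76 more days for healthy men and 69 for hepatic impaired men, and must follow any reported pregnancy to its outcome.
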